4.8. Interim Analyses

The analysis method for the primary efficacy endpoint described in Section **Error! Reference source not found.** Primary Endpoints/Estimands Analysis will be used for the interim analysis.

The interim analysis will be conducted such that the ongoing study integrity is maintained. Some team members, who are responsible for providing the interim analysis results, will be unblinded to the individual treatment group assignments. Interim analysis results will not be shared with investigators, participants, or the study team who are involved in the conduct of the study before the final database lock.

Analyses for the primary database lock will be conducted when all participants have completed the Double-blind Treatment Period or discontinued treatment.

An interim analysis of the safety and efficacy data may be conducted prior to database lock, to support planning activities. This will be done when approximately 40% to 60% of participants have completed Period 1 (double-blind treatment) or have discontinued treatment.

A Bayesian posterior probability rule will be used to assess the efficacy of 700 mg vs placebo for DAS28-CRP for period 1. Two pairwise comparisons will be made and the corresponding posterior probability will be provided. Specifically, the pairwise comparisons will be 700mg vs placebo and 300mg vs placebo. The prior distribution for each arm will be assumed to a normal distribution with mean of 0 and standard deviation of 10. The error parameter will use an Inverse-Gamma distribution assuming central value of 10 and weight of 1. The posterior probabilities will be provided for each of the CSF's for both pairwise comparisons at the interim and also at the final analysis.

All interim analyses will be used to support planning activities associated with the clinical development program and to aid in the development of PK/PD modeling. Since the study may terminate early only for safety and/or futility, no adjustment of type I error will be performed.

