6.3. Measures to Minimize Bias: Randomization and Blinding

To preserve the blinding of the study, a minimum number of Lilly personnel who are not directly involved with investigational sites will see the randomization table and treatment assignments before the study is complete.

Joint, disease activity, and safety assessments

Joint Assessor

To prevent potential bias due to observed efficacy or laboratory changes, a “dual assessor” approach will be used to evaluate efficacy and safety. The Joint Assessor (or designee) should be a rheumatologist or skilled arthritis assessor. The Joint Assessor will be responsible for completing the joint counts. To ensure consistent joint evaluation throughout the trial, individual participants should be evaluated by the same Joint Assessor for all study visits. The Joint Assessor must not access or discuss with the participant the patient-reported assessments, Physician’s Global Assessment of Disease Activity (PhGADA_VAS), and safety assessments.

Safety Assessor

The Safety Assessor (or designee) should be a rheumatologist (or medically qualified physician) and will have access to both safety and efficacy data. The Safety Assessor may be the principal investigator. The Safety Assessor will be responsible for completing the PhGADA_VAS. To ensure consistent PhGADA_VAS throughout the trial, the instrument should be evaluated by the same physician at all study visits. The Safety Assessor will have access to source documents, laboratory results, and electronic case report forms (eCRFs) and will be responsible for making treatment decisions based on a participant’s clinical response and laboratory parameters.

Method of treatment assignment

Assignment to treatment groups will be determined by a computer-generated random sequence using an interactive web-response system (IWRS).

Participants will be stratified by prior use of csDMARD only or by tsDMARD/bDMARDs use (yes versus no).

Emergency unblinding

In case of an emergency, the investigator has the sole responsibility for determining if unblinding of a participant's treatment assignment is warranted. Participant safety must always be the first consideration in making such a determination. If a participant's treatment assignment is unblinded, the sponsor must be notified immediately.

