9.5. Interim Analyses

Analyses for the primary database lock will be conducted as described in Section 9.4 when all participants have completed the double-blind treatment period or discontinued treatment.

One interim analysis of the safety and efficacy data will be planned prior to database lock, to support planning activities. This will be done when approximately 40% to 60% of participants have completed Period 1 (double-blind treatment) or have discontinued treatment. Bayesian posterior probabilities will be calculated to assess the efficacy of LY3462817 700 mg versus placebo for DAS28-CRP for Period 1 at the interim analysis. The decision rules based upon the posterior probability results will help in deciding whether to support further clinical development of LY3462817. Additionally, this interim analysis will aid in the development of PK/PD modeling.

Other interim analyses may be conducted as needed. All interim analyses will be used to support planning activities associated with the clinical development program and to aid in the development of PK/PD modeling. Since the study may terminate early only for safety and/or futility, no adjustment of type I error will be performed. Information about interim futility and decision rules will be provided in the SAP.

Internal assessment committee

Assessment of unblinded interim data will be conducted by an internal assessment committee (AC) with a limited number of prespecified members who do not have direct site contact or data entry or validation responsibilities (see Section 10.1.5, Appendix 1). Unblinding details will be specified in the unblinding plan section of the SAP or in a separate unblinding document. Information that may unblind the study during the analyses will not be reported to study sites or blinded study team until the study has been unblinded. Study sites will receive information about interim results only if they need to know for the safety of their participants.

Evaluation of unblinded safety data by the internal AC will occur if any of the following events are observed following review by the blinded safety review team:

- three or more participants experience TEAEs in the same system organ class, and these TEAEs assessed as severe by the investigator and are judged as related to blinded study treatment by the investigator.
- a malignancy SAE occurs during the study.

Pending the evaluation by the internal AC, enrollment and/or further dosing may be stopped.

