4.3.2. Main analytical approach

Observed values at baseline and changes from baseline to Week 12 endpoint in DAS28-CRP will be summarized by treatment arm and provided as listing.

A restricted maximum likelihood based, MMRM analysis will be used to analyze the primary endpoint. The MMRM model will include treatment, strata (previous RA therapy population), baseline value, visit, treatment-by-visit interaction in the model as fixed factors, and patient as a random factor. An unstructured covariance matrix will be used to model the within-subject errors. If this analysis fails to converge, other structures will be tested (in this order: Toeplitz, Autoregressive with heterogeneity, and Compound Symmetry). The Kenward-Roger approximation will be used to estimate denominator degrees of freedom. Significance tests will be based on least squares means and Type III tests. The data on or after the treatment discontinuation will not be included in MMRM analysis.

For participants who discontinue study intervention and/or receive rescue therapy, post-discontinuation or post-rescue observations will not be included.

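### SAP 4.8 specifies the Bayesian posterior-probability model with arm means and one error term, without the baseline DAS28-CRP and randomisation stratum of the primary MMRM, and does not reconcile this with its own opening sentence

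*SAP*

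**What the plan says.** The primary analysis in SAP 4.3.2 is adjusted: "The MMRM model will include treatment, strata (previous RA therapy population), baseline value, visit, treatment-by-visit interaction in the model as fixed factors". The stratum in that model is the factor that stratifies randomisation in Protocol 6.3 (csDMARD experience only, or tsDMARD/bDMARD use).

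SAP 4.8 makes two statements about the interim method. Its first sentence, through a broken cross-reference, carries over "The analysis method for the primary efficacy endpoint described in Section" (the number is missing, but the title named is that of the primary endpoint analysis). It then describes a Bayesian rule for 700 mg versus placebo and 300 mg versus placebo. The whole specification of that model is the prior on each arm, "The prior distribution for each arm will be assumed to a normal distribution with mean of 0 and standard deviation of 10", and the prior on the error, "The error parameter will use an Inverse-Gamma distribution assuming central value of 10 and weight of 1". Baseline, stratum, visit and within-participant covariance are not mentioned.

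On use, Protocol 9.5 says "The decision rules based upon the posterior probability results will help in deciding whether to support further clinical development of LY3462817", and SAP 4.8 says that the probabilities are supplied "for both pairwise comparisons at the interim and also at the final analysis". On timing, "This will be done when approximately 40% to 60% of participants have completed Period 1 (double-blind treatment) or have discontinued treatment".

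**The concern.** The two statements in SAP 4.8 do not describe the same analysis. The primary method is a REML-based MMRM, which does not itself produce a posterior probability. A Bayesian version of it would need priors for the baseline slope, the stratum effect, the visit effects and the covariance of the four post-baseline Period 1 visits (Weeks 2, 4, 8 and 12). None is given. A programmer who follows the listed priors would fit one mean per arm and one residual variance, and so leave out two covariates that are already collected and already in the primary model.

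Elsewhere the SAP names covariates even for exploratory work: the MRI ANCOVA (4.5.5), the remission and low-disease-activity models (4.5.1 to 4.5.4) and the subgroup models (4.7.2). The silence in 4.8 therefore stands out.

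Two things are at stake: precision at a look with very few placebo participants, and a modelling choice left open in the analysis that informs a development decision. Protocol 9.5 has the SAP finalised before any unblinding in order to minimise bias, and that works only if the model is fully stated.

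**Working it through.** **Inputs.** From the sample size sections (Protocol 9.2, SAP 5): 40 participants on 700 mg and 20 on placebo; mean changes -1.80 and -0.75, so a difference of 1.05; SD 1.25; two-sided alpha 0.05. Allocation is 2:1:1 and the interim comes at 40% to 60% of participants. The documents do not give the share of variance explained by baseline and stratum (R²), so it is varied.

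**1. The plan's own figure.** SE = 1.25 × √(1/40 + 1/20) = 0.342, and 1.05/0.342 = 3.07. With 58 df the noncentral t gives 85.5% power (normal approximation 86.6%). This agrees with the stated value of more than 80%.

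**2. Interim numbers.** If the allocation ratio holds, 40% of 80 gives 16 versus 8, 50% gives 20 versus 10, and 60% gives 24 versus 12 (700 mg versus placebo). At the final analysis it is 40 versus 20.

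**3. What the arm priors do.** With 8 placebo participants, the Normal(0, SD 10) prior shrinks the arm mean by (1.25²/8)/(1.25²/8 + 100) = 0.2%. The posterior difference is therefore practically the raw difference in observed means.

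**4. Effect of adjustment on the SE.** With N the total in the two arms and two covariates estimated,

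SE(adjusted) = SE(unadjusted) × √(1 − R²) × √(1 + 2/(N − 5)).

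The last factor is the expected cost of estimating two coefficients. Setting the product of the two factors to 1 gives a break-even R² of 2/(N − 3).

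| 700 mg v placebo | Unadjusted SE | R²=0 | 0.1 | 0.2 | 0.3 | 0.4 | Break-even R² |
|---|---|---|---|---|---|---|---|
| 16 v 8 | 0.541 | 0.569 | 0.540 | 0.509 | 0.476 | 0.441 | 2/21 = 9.5% |
| 24 v 12 | 0.442 | 0.456 | 0.433 | 0.408 | 0.381 | 0.353 | 2/33 = 6.1% |
| 40 v 20 | 0.342 | 0.348 | 0.331 | 0.312 | 0.292 | 0.270 | 2/57 = 3.5% |

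Over R² from 0 to 0.4, the SE at 16 versus 8 changes by +5% to −19%.

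**5. Illustrative power.** This uses a two-sided 0.05 t-test at the planning effect, with SD 1.25 read as unadjusted. R² = ρ², where ρ is an assumed baseline-change correlation that stands for all the explained variance. Noncentrality = 1.05/SE(adjusted), and df = N − 4 (N − 2 unadjusted).

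| 700 mg v placebo | Unadjusted | ρ=0 | ρ=0.3 | ρ=0.5 |
|---|---|---|---|---|
| 16 v 8 | 45.8% | 42.0% | 45.3% | 52.7% |
| 20 v 10 | 55.3% | 52.0% | 55.8% | 64.1% |
| 24 v 12 | 63.6% | 60.8% | 64.8% | 73.2% |
| 40 v 20 | 85.5% | 84.2% | 87.4% | 92.8% |

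At 20 versus 10 with ρ = 0.5, SE(adjusted) = 0.484 × √0.75 × √(1 + 2/25) = 0.436, and 1.05/0.436 = 2.41 on 26 df gives 64.1%.

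**The case against.** **Covariates may be intended.** The opening sentence of SAP 4.8 invokes the primary method, which contains them, and priors that are not listed show an incomplete specification rather than a decision to leave terms out. This stands in part: a reader might infer that the sponsor chose an unadjusted model, and the text does not establish that. Nor does it establish that the model ignores Weeks 2 to 8, because it refers to DAS28-CRP for Period 1 without limiting the data to Week 12. But the sentence does not supply the missing terms or priors, so the same edit is needed on either reading.

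**The posterior is not decisive.** A reader might infer that it drives both the interim and the final decision. Protocol 9.5 says only that the rules help in deciding. At the final analysis the primary inference is the adjusted MMRM, and the posterior probabilities are reported without a stated final rule. The count of 8 to 12 placebo participants applies to the interim alone. All of this stands.

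**Wasted precision is not shown.** It depends on an R² that the documents do not give, and at 16 versus 8 with ρ = 0.3 adjustment loses slightly. If SD 1.25 is already a residual SD, the power gain in step 5 is counted twice. Nor is chance baseline imbalance a separate bias: it is ordinary sampling error, already inside the unadjusted SE. These points stand, and they make the gain conditional.

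**The power figures are not those of the SAP's rule.** That is correct. SAP 4.8 refers to CSFs without giving values, and the calculation does not use its error prior. The t-test only illustrates the size of the effect.

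**Conclusion.** The concern holds as a matter of specification, with a conditional gain in precision. The Bayesian model in SAP 4.8 has no stated term for baseline DAS28-CRP or the randomisation stratum, and the section does not reconcile this with its opening sentence. Followed as written, it is an unadjusted comparison of arm means.

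At the interim, adjustment improves expected precision if the two covariates together explain more than about 10% of the variance at 16 versus 8, or about 6% at 24 versus 12. At 20 versus 10 and an assumed correlation of 0.5, illustrative power rises by about 9 points; at 0.3 the change is about half a point. These figures rest on the planning effect, on SD 1.25 being unadjusted, on a two-sided 0.05 test standing in for an unstated posterior threshold, and on the 2:1:1 ratio holding at the interim. The documents do not support a claim that the unadjusted comparison is biased or invalid.

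**What to change.** In SAP 4.8, state that the Bayesian model for Week 12 change in DAS28-CRP includes baseline DAS28-CRP and previous RA therapy population as covariates, with vague normal priors on both coefficients, and that the same model gives the interim and the final posterior probabilities. Repair the cross-reference to the primary analysis and say how the opening sentence relates to the Bayesian rule. If a repeated-measures model is preferred, state its visit and treatment-by-visit terms, their priors, and the prior for the within-participant covariance.

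The cost is one paragraph of SAP text and two extra model terms, with no new data. The statistical price is about two degrees of freedom. If baseline and stratum explained nothing, illustrative power would fall by about 3 points at 20 versus 10 (55.3% to 52.0%) and about 4 points at 16 versus 8 (45.8% to 42.0%). A repeated-measures version costs more to specify, because of the covariance prior.

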4.8.1. Data Monitoring Committee (DMC) or Other Review Board

There will be no DMC in this study. An Internal Assessment Committee (IAC) will be used to conduct the interim analysis. The IAC will consist of a limited number of prespecified members not part of the blinded study team who do not have direct site contact or data entry or validation responsibilities. Further details will be provided in the IAC charter.

4.9. Changes to Protocol-Planned Analyses

There is no change to protocol-planned analyses.

5. Sample Size Determination

Approximately 80 participants will be randomly assigned to study intervention. At the completion of the study, approximately 40 participants will have been randomized to LY3462817 700 mg and 20 participants will have been randomized to LY3462817 300 mg and placebo during the double-blind treatment. All randomized participants in FAS will be considered evaluable.

Assuming -1.80 and -0.75 as the DAS28-CRP change from baseline for LY3462817 700 mg and placebo, respectively, with standard deviation equal to 1.25, a 2-sided t-test with alpha = 0.05 has greater than 80% power to detect a statistically-significant difference in DAS28-CRP change from baseline at Week 12.

6. Supporting Documentation

6.1. Appendix 1: Demographic and Baseline Characteristics

Demographics and baseline characteristics will be summarized for all patients in the FAS by treatment arm (LY3462817 300 mg, LY3462817 700 mg, and placebo) and overall and provided as listing:

Demographics:

- Sex (Female, Male)
- Race (White, Black or African American, Asian, American Indian or Alaska Native, Native Hawaiian or Other Pacific Islander, and their subcategories)
- Ethnicity (Hispanic or Latino, Not Hispanic or Latino, Not Reported, and their subcategories)
- Age (years)
- Baseline Weight (kg) and Height (cm)
- Baseline BMI (kg/m2)

Baseline characteristics:

- DAS28-CRP
- TJC
- SJC
- PhGADA_VAS (VAS)
- PaGADA_VAS (VAS)
- Patient's global assessment of arthritis pain (VAS)
- Patient's assessment of physical function (HAQ-DI)
- SDAI
- CDAI

6.2. Appendix 2: Treatment Compliance

Treatment compliance will not be calculated in this study.

6.3. Appendix 3: Clinical Trial Registry Analyses

Additional analyses will be performed for the purpose of fulfilling the Clinical Trial Registry (CTR) requirements.

Analyses provided for the CTR requirements include the following:

Summary of adverse events, provided as a dataset which will be converted to an XML file. Both Serious Adverse Events and ‘Other’ Adverse Events are summarized: by treatment group, by MedDRA preferred term.

- An adverse event is considered ‘Serious’ whether or not it is a treatment emergent adverse event (TEAE).
- An adverse event is considered in the ‘Other’ category if it is both a TEAE and is not serious. For each Serious AE and ‘Other’ AE, for each term and treatment group, the following are provided:
 - the number of participants at risk of an event
 - the number of participants who experienced each event term
 - the number of events experienced.
- Consistent with www.ClinicalTrials.gov requirements, ‘Other’ AEs that occur in fewer than 5% of patients/subjects in every treatment group may not be included if a 5% threshold is chosen (5% is the minimum threshold).
- AE reporting is consistent with other document disclosures for example, the CSR, manuscripts, and so forth.

Leo Document ID = 30346ea8-53e4-4f6d-b82d-3880749a9adf

Approver: PPD

Approval Date & Time: 23-Dec-2020 15:41:48 GMT

Signature meaning: Approved
